# Protocol and Statistical Analysis Plan

## Study Protocol

### Objectives

This research tests the effects of the mere presence of guns in the mass media (e.g. movies, video games, TV programs) on children. We predict that seeing guns in the mass media will increase subsequent aggression, and will lead to more positive attitudes about guns.

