### Experiment

Participants will be children 8-12 years old. Children will be tested in pairs. Each child will bring a sibling, relative, or friend to the study. Participants and partners will each receive a \$25 gift card. The design is a 2 (watch vs. play) by 3 (non-violent, violent with swords, violent with guns) between-subjects design. The outcome variables are the time spent handling a gun (in seconds), the number of times the trigger is pulled, and the number of times the trigger is pulled while pointing the handgun at oneself or another. After filling out a pre-test survey measuring trait aggression and media diet, one participant will be randomly assigned to play a video game while the other watches. The video game participants will play is a modified version of *Minecraft*. The participant pairs will be randomly assigned to one of three conditions: a non-violent condition with no weapons and no monsters, a violent condition with swords and monsters, and a violent condition with guns and monsters. Participants will play for 20 minutes, after which they will fill out a survey measuring their familiarity with *Minecraft* and their opinion toward the game.

After completing the survey, participants will be placed in a room containing games and toys, with hidden cameras. Participants will be told that they can play with any of the games and toys in the room

for the next 20 minutes. The toys and games will be in two drawers of a cabinet, while the bottommost drawer will contain two Sig Sauer P250 handguns. The handguns have been disabled and are unable to fire. In addition, a counter is placed inside the magazine well to count the number of times the trigger is depressed with enough force to discharge the handgun. This allows us to distinguish reliably the children who pull the trigger from those who handle the gun but do not pull the trigger. Parents will be asked to predict whether their child will handle the real gun and pull the trigger. The researcher and the parents will be able to watch the session via a monitor in a control room. After 20 minutes, the participants will fill out a survey on their attitudes toward guns. A thorough debriefing will follow.

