We predict that participants who play the game with guns will handle the gun longer, pull the trigger more times, and point the gun at oneself or another and pull the trigger more times than participants in the other conditions. One week after a child participates in Experiment 3, the researcher will call or email the parent to follow up.

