### **Behavioral Measure of Aggression**

Experiments 1 and 2 will use a measure of aggression that has been successfully used for children about this age in our previous research.ix,x Participants will complete a 25-trial competitive reaction time task with an ostensible partner of the same sex in which the winner can blast the loser with loud noise through headphones. The noise is a mixture of noises that most people hate (e.g., fingernails scratching a chalkboard, dentist drills, sirens). The noise levels range from *Level 1*=60 decibels to *Level 10*=105 decibels (about the same level as a fire alarm). Participants will be told that lose levels 8, 9, 10 can cause "permanent hearing damage to their partner."xi The noise levels are well within Occupational Safety and Health Administration (OSHA) safety levels (i.e., 120 decibels). The threshold of pain for the human ear is 140 decibels. Because decibels are measured on a logarithm scale, level 105 decibels is unpleasant but not painful or harmful. A non-aggressive no-noise option (*Level 0*) is also provided. The winner can also determine the duration of the loser's suffering by controlling the noise duration (*Level 1*=0.5 sec to *Level 10*=5 sec). The participant wins half of the trials (randomly determined). The ostensible partner set random noise intensities and durations across the 25 trials. Basically, within the ethical limits of the laboratory, participants control a weapon that can be used to blast their partner with unpleasant noise. A thorough debriefing will follow that we have successfully used in previous studies in which children are

exposed to violent media. The parent will also be present during the debriefing. The researcher will read the debriefing to the child and answer any questions he or she has.

For each of the dependent variables, we predict a main effect for violent content, a main effect for the presence of guns, and an interaction between violent content and the presence of guns. Specifically, we predict the highest levels of pro-gun attitudes and aggression among participants who see a violent clip containing guns.

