## Statistical Analysis Plan

Data will be collected in three ways: parental consent is collected directly by Qualtrics; the participants' survey responses are done by hand on paper, and the participants' handling of the handguns is recorded as video. After the conclusion of the study, the paper responses will be uploaded by the research staff into a Qualtrics survey. The videos will be content analyzed by trained research assistants who observe the participants' behavior, verify the trigger pull count, and note if the trigger is depressed while the handguns are pointed at oneself or the other participant. At this point, the data can be merged into a single dataframe for validation and cleaning. Cleaning will be done in Excel and R.

Once the data has been cleaned, the variables will each be examined via summary statistics and visually. If necessary, variables will be transformed to conform to the assumptions of the statistical tests, the Cronbach's alpha of the survey batteries will be calculated, potential outliers will be identified, and preliminary bivariate and chi-squared tests will be run on the outcome variables. In addition, the three conditions will be tested for differences in the subjects along the measured variables.

After this, the dataframe will be imported into STATA to perform a generalized estimated equation (GEE) with an exchangeable correlation structure was used to analyze data, with pairs as unit of analysis. All outcome variables will be measured with a negative binomial log-link model. First, each outcome variable will be tested with the condition as the sole predictor variable. Next, each control variable (trait aggression, attitude toward guns, etc.) will be tested along with the condition. Finally, the full model will include condition and all of the control variables. The research team will find the model of best fit, though only the reduced (condition only) and full models (condition, gender, age, whether the participant had taken a firearm safety course, if there is a firearm in the home, attitudes toward guns, trait aggression, consumption of violent media, parental estimation of child's interest in firearms) will be reported.

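### The full model adjusts for gun attitudes measured only after the game and the gun session, and the plan does not say whether it or the condition-only model decides

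*Combined protocol and SAP*

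**What the plan says.** **Timing.** The Experiment section starts the session with a survey of two constructs: "After filling out a pre-test survey measuring trait aggression and media diet". The 20-minute game and the 20 minutes in the room with the handguns follow. Only then come the child's gun attitudes: "After 20 minutes, the participants will fill out a survey on their attitudes toward guns". The Attitudes Toward Guns section describes the questionnaire but gives no baseline administration. The gun-related measure it places before the experiment is the parent's rating of the child's interest, which is a separate covariate.

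**Expected effect.** The Objectives predict that seeing guns in the media "will lead to more positive attitudes about guns".

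**Use.** The Statistical Analysis Plan treats attitudes as a control variable, first alongside condition alone and then in the full model, whose list includes "if there is a firearm in the home, attitudes toward guns, trait aggression, consumption of violent media". The team will search for the best-fitting model, "though only the reduced (condition only) and full models" are to be reported. Neither is named as the one that decides.

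**Attitudes as an outcome.** No outcome model for attitudes is planned. The nearest thing is a general check in which "the three conditions will be tested for differences in the subjects along the measured variables".

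**The concern.** Randomisation protects the comparison of conditions as long as the model adjusts only for things that condition cannot have changed. Attitudes recorded after both exposure and outcome fail that test in three ways. They may carry part of the effect (mediator). They may be changed by the handling itself (the outcome feeds back into the covariate). They may share an unmeasured cause with handling, so that holding them fixed creates an association between condition and that cause.

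Under the study's own hypothesis, the two reported models therefore estimate different quantities. They can disagree, and nothing in the plan says which carries the conclusion. A real effect may look smaller or non-significant in the adjusted table, and a null effect may look protective.

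**Working it through.** **Which full-model covariates are fixed before the game?** Gender, age, safety course, firearm in the home, trait aggression, violent media consumption and parent-rated interest are facts or measurements that precede exposure. Attitudes toward guns are the only one of the eight that does not.

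**The plan's own figure.** The Power Analysis gives 64 per group. A two-sample t-test with standardised difference 0.5 (assumed reading of a medium effect), two-sided .05 and power .80 needs 63.8, so 64; power at 64 is 0.801. Then 3 × 64 = 192, which reproduces. Both children in a pair share a condition, so there are 192/2 = 96 pairs and 96/3 = 32 pairs per condition. The concern does not depend on this figure; it only sets the size of the runs in (d).

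**Assumed, because the documents give no values.** d is the shift in attitudes due to condition, in SD. g is the rate multiplier per SD of attitude. Data are negative binomial with log link, dispersion 1 and baseline mean 3. Large-sample runs used 300,000 children per scenario. The adjusted model in all runs adds only the attitude covariate to condition.

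**(a) Attitudes as mediator, true ratio 2.0.** The total ratio is the direct ratio times g^d. The full model holds attitudes fixed and returns the direct part, 2.0 / g^d:

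| | g = 1.25 | g = 1.5 | g = 2.0 |
|---|---|---|---|
| d = 0 | 2.00 | 2.00 | 2.00 |
| d = 0.2 | 1.91 | 1.84 | 1.74 |
| d = 0.5 | 1.79 | 1.63 | 1.41 |

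Simulation agreed to within about 0.01. The limiting case is an effect that runs wholly through attitudes. With d = 0.5 and a log-rate slope of 0.5 per SD, the condition-only ratio is exp(0.5 × 0.5) = 1.28 and the adjusted ratio is 1.00.

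**(b) Handling changes attitudes, with no other path (simulation).** With correlations of 0.1, 0.3 and 0.5, a true ratio of 2.0 becomes 1.99, 1.89 and 1.72. A true ratio of 1.0 stays at 1.00.

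**(c) Handling unaffected (true ratio 1.0), unmeasured trait shared by attitudes and handling.** Let the trait load λ on attitudes (unit SD within condition) and 0.7 on the log mean. At a fixed attitude score, children in the shifted condition have a trait value lower by λd, so the adjusted ratio is exp(−0.7 × λ × d):

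| | λ = 0.3 | λ = 0.5 | λ = 0.7 |
|---|---|---|---|
| d = 0 | 1.00 | 1.00 | 1.00 |
| d = 0.2 | 0.96 | 0.93 | 0.91 |
| d = 0.5 | 0.90 | 0.84 | 0.78 |

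Simulation again agreed to within about 0.01.

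**(d) At the planned size, true ratio 2.0.** 96 pairs in three conditions; negative binomial GEE, exchangeable within pair; pair-effect SD 0.5 on the log scale; guns versus non-violent at two-sided .05; 250 runs per scenario (Monte Carlo error about 3 percentage points). The last column is full − (condition-only − discordant), for example 80 − (75 − 5) = 10.

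| d, g | Condition-only significant | Full significant | Only condition-only significant | Only full significant |
|---|---|---|---|---|
| 0, 1.5 | 75% | 80% | 5% | 10% |
| 0.2, 1.5 | 70% | 67% | 8% | 5% |
| 0.5, 1.5 | 72% | 51% | 21% | 0% |
| 0.5, 2.0 | 61% | 28% | 34% | 1% |

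**The case against.** The valid analysis is already planned: condition alone is fitted first for each outcome and its result will be reported. Because reporting is limited to the reduced and full models, the best-fit search cannot displace it. The harm is confined to how a second, disclosed model is read. This stands and limits the severity, but it does not settle which result carries the conclusion when the two differ.

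Attitudes may not be an outcome of this experiment. Its listed outcomes are behavioural, and its prediction is that children who play with guns will "handle the gun longer, pull the trigger more times". The text then calls it Experiment 3. The other attitude prediction, "we predict the highest levels of pro-gun attitudes and aggression among participants who see a violent clip containing guns", follows an aggression measure assigned to Experiments 1 and 2. Only the general Objectives, which do name video games, point to this experiment. The absence of an attitude analysis is therefore a point to clarify. The adjustment problem remains either way, because it rests on timing.

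The illustrations are assumption throughout, and the simulated full model omits the other seven covariates, some of which would absorb part of a shared trait. In separate runs of (c) at d = 0.5, adding one pre-game proxy correlated 0.7 with the trait moved the ratio from 0.91 to 0.95, 0.83 to 0.90 and 0.78 to 0.84 for the three loadings. A proxy correlated 0.3 changed it by only about 0.01. So (c) is at the upper end: the bias shrinks but does not vanish.

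In (d), the models disagree in about 15% of runs (5% + 10%) even with no shift, and the net loss at d = 0.2 is 3 points, about the simulation error. Only the d = 0.5 rows show a clear loss.

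Finally, attitudes might be a stable trait. The plan cannot show this, since it has no baseline score.

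**Conclusion.** The concern holds and should be fixed. That attitudes are measured only after exposure and outcome, are used as a control, and appear in one of two reported models with no stated priority follows from the text without any assumption.

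The size does not. At a true ratio of 2.0, (a) gives 1.74 to 1.91 for a 0.2 SD shift and 1.41 to 1.79 for a 0.5 SD shift. Feedback from handling alone gives 1.72 to 1.99. With handling unaffected, a shared trait can produce a spurious ratio of about 0.78 to 0.96. If condition shifts neither attitudes nor handling, there is no bias. Confidence is high on the estimand and low on how far the actual results would move.

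**What to change.** 1. Delete attitudes toward guns from the control variables and from the full model, leaving the seven covariates fixed before the game. Label any attitude-adjusted model exploratory.
2. State which reported model is decisive for each outcome, for example the condition-only model.
3. State whether the attitude prediction in the Objectives applies to this experiment. If it does, analyse the attitude score as an outcome by condition, specifying the total or the three subscales. Use a pair-clustered model suited to a scale score, for example an identity-link GEE. Adjustment for parent-rated interest, a related baseline proxy, is optional. Say that the result reflects the game plus the gun session, since the survey follows both.

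The cost is SAP wording and at most one added model, or one per subscale, on data already collected. No extra participants or procedures are needed. If condition does not shift attitudes, some precision is lost: the no-shift row of (d), 75% against 80%, shows the order of it.
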